10.2 Study Period

Day 0 and prior (diagnosis): occurring at least within 48 hours prior to MSR

- Randomization
- Initiate AED, per Section [7.1.1](#) (LCM 100mg BID or LEV 1000mg BID)
- Characterize seizure type, if applicable, (i.e., simple partial, complex partial, or generalized)

Week 0-6

- Management of AEDs for any seizure events or adverse events will be left at the discretion of the treating physician. If side effects occur, adjusting dosing of current AED before changing AEDs is recommended.

Week 6-10: at the first planned post-procedure visit (LGG or brain metastasis) or first visit after radiation (HGG), the following study endpoint data will be collected only for the 30-day post-procedure time period

- Collection of calendar, if not already obtained from the REDcap database
- CMP and CBC with differential to assess resolution of toxicity
- AESI (please see Section [7.1.4](#))
- Number of readmissions, ED visits, provider communications during the 30-day post-procedure phase
- Number of dose adjustments, additions or discontinuations of AED(s) during the 30-day post-procedure phase
- Initiate weaning of the AED per discretion of the treating physician, for example:
 - LCM 100/50mg x1 week, 50/50mg x 1 week, 50mg daily x 1 week, then off
 - LEV 1000/500mg x1 week, 500/500mg x 1 week, 500mg daily x 1 week, then off

10.3 Follow-up Period

Subjects will be followed for seizure-related healthcare encounters at the times described above (See Section [10.2](#)). Adverse events will be collected and recorded for the first 30 days post-procedure (See Sections [7.1.3](#) and [7.1.4](#) for details).

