6 OBJECTIVES AND ENDPOINTS

Table 1: Objectives and Endpoints

	Objective	Endpoint	Analysis
Primary	Assess the impact of LCM, LEV or no AED in patients with suspected glioma (WHO Gr I-IV) or brain metastasis on ED visits and readmissions within 30 days of MSR	Percentage of patients with an ED visit or hospital readmission within 30 days of MSR	See Section 13.4
Secondary	Assess the safety and tolerability profile of LCM and LEV	Percentage of patients who experience an adverse event of special interest within the first 30 days after MSR	See Section 13.5
Exploratory	Describe the duration of admission stays among patients treated prophylactically with LCM, LEV, or no AED	Median duration of initial admission stay for MSR	See Section 13.6.1
Exploratory	Describe the number of provider communications (email, telephone, or additional clinical visits) among patients treated prophylactically with LCM, LEV, or no AED	Frequency distribution for the number of provider communications (email, telephone, or additional clinical visits) that occurred within 30 days of MSR.	See Section 13.6.2
Exploratory	Describe the usage of intraoperative AED	Percentage of patients requiring intraoperative AED	See Section 13.6.3
Exploratory	Assess the impact of LCM, LEV, or no AED on post-procedure seizure occurrence	Percentage of patients experiencing post-procedure seizures during the 30-day post-operative phase.	See Section 13.6.4
Exploratory	Describe the frequency of changes in AED dosage, type of AED, addition or discontinuation of AED	The frequency of changes in dosages, type of AED, addition or discontinuation of AED that occur within 30 days of MSR	See Section 13.6.5
Exploratory	Evaluate patient risk factors for post-procedure seizure	Statistically significant association of specific risk factors with rate of post-procedure seizure during the 30-day post-procedure phase	See Section 13.5.6

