7.1.3 Post-procedure data collection

Approximately 6-10 weeks after the procedure (for LGG or recurrent high grade glioma or brain metastasis) or first visit after radiation [for newly-diagnosed or transformed high grade glioma (HGG)], the following data will be obtained: admission duration for the MSR, any seizure activity, any readmissions, ED visits, and provider communications (telephone, email, and additional clinic encounters, etc.), as well as for tolerance of the AED by clinical history and neurological examination. Reasons for readmission and ED visits will also be noted. All of these data are only obtained if relevant during the 30-day post-procedure time. Patients will be provided a physical calendar to document any of the above, or provided access to the Research Electronic Data Capture™ (REDCap™) calendar, based on the patient's preference.

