10 SCREENING AND ON-STUDY TESTS AND PROCEDURES

Table 2: Schedule of Events

Description	Screening at pre-operative visit up to 48 hours prior to MSR	First post-procedure visit (LGG) or first visit after radiation (HGG)
Week		6-10*
Day	0	
General Evaluations		
Physical Exam	X	X
Neurologic Exam	X	X
Evaluation as candidate for MSR	X	
Adverse Events		X
Laboratory Evaluations		
CBC with differential	X	X
CMP	X	X
Urine Pregnancy Test	X	
Disease Evaluations		
Seizure-related readmissions, ED visits, provider communications, duration of admission for MSR		X

*While patients will be assessed between 6-10 weeks post-procedure, only endpoint data pertaining to the first 30 days post-procedure will be recorded in the source documentation and in the database.

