The protocol assessed the need for AED prophylaxis during the post-procedure period in patients undergoing MSR for a suspected diagnosis of glioma (WHO grade I-IV) or brain metastasis. There will be three arms to the study – patients were randomized to LCM, LEV, or control (no AED). The AED can be initiated anytime within 48 hours before an MSR incision. Subjects were followed for seizure-related healthcare encounters. Adverse events were collected and recorded for the first 30 days post-procedure.

5. Study Population:

Inclusion criteria

1. Patients with a suspected diagnosis of new, recurrent, or transformed glioma (WHO grade I-IV) or brain metastasis scheduled for MSR at DUMC;
2. Safe for surgery per treating neurosurgeon;
3. Due to the potential implications of the treatment on the developing CNS, all patients must be ≥ 18 years of age at the time of entry into the study;
4. Laboratory Studies:
 - a. Total bilirubin, Serum Glutamic Oxaloacetic Transaminase (SGOT), Serum Glutamic Pyruvic Transaminase (SGPT), Alkaline Phosphatase (ALK) $\leq 1.5 \times$ upper limit of normal (ULN)
 - b. Creatinine ≤ 1.5
5. A signed informed consent form approved by the Duke University Institutional Review Board (IRB) will be required for patient enrollment into the study. Patients or their Legally Authorized Representative (LAR) must be able to read and understand the informed consent document and must sign the informed consent indicating that they are aware of the investigational nature of this study. Treating physicians at the time the protocol is presented can determine based on their clinical judgment whether patients lack the capacity and require a LAR to sign the consent form.
6. Patients of childbearing potential or with partners of child-bearing potential must agree to practice recommended contraceptive methods to prevent pregnancy during treatment and for 1 month after the last dose of AED for women and men.

Exclusion criteria

1. Pregnant or need to breastfeed during the study period (Negative urine β -HCG test required), or unable to maintain use of contraception while on the study and for 1 month after the last dose of AED;

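### Protocol 10.3, SAP section 4 and arguably Table 2 limit follow-up to seizure-related encounters, while the primary endpoint has no cause restriction

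*Protocol*

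**What the plan says.** **Restricted wording.** Protocol 10.3: "Subjects will be followed for seizure-related healthcare encounters at the times described above", with a cross-reference to 10.2. SAP section 4 (Study Design & Procedures): "Subjects were followed for seizure-related healthcare encounters". The encounter row of the Schedule of Events (Protocol section 10, Table 2) reads "Seizure-related readmissions, ED visits, provider communications, duration of admission for MSR".

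**Unrestricted wording.** Protocol Table 1 defines the primary endpoint as "Percentage of patients with an ED visit or hospital readmission within 30 days of MSR". Sections 13.4, 13.4.1, 13.4.2 (P1 and P2), 13.7 (the Z statistic) and SAP section 6 (variables admitted_ed and hospitalized) likewise name no cause. Protocol 7.1.3 collects "any seizure activity, any readmissions, ED visits, and provider communications" and adds "Reasons for readmission and ED visits will also be noted". Protocol 10.2 says "the following study endpoint data will be collected only for the 30-day post-procedure time period", and its list includes "Number of readmissions, ED visits, provider communications during the 30-day post-procedure phase". The 12% rate behind the sample size in 13.8 is also given without a cause, and the rule in 13.4.3 that counts a death as an event names none.

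**The concern.** The follow-up text tells staff which encounters to look for, and the endpoint text tells the analyst which encounters count. Here the two differ in scope. Someone working from 10.3 or SAP section 4 alone could leave out an ED visit for a wound problem, or a readmission for dizziness or a behavioural reaction to an AED. Each of these counts under 13.4.1.

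The side-effect encounters matter most. Section 5.2.9 sets out to weigh the benefit of prophylaxis against its side effects, and it makes readmissions and ED visits the primary outcome; seizure variables are deliberately exploratory.

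A restricted rule would also need someone to decide whether each encounter was related to a seizure. The trial has a no-AED arm and describes no blinding, so that judgment could be made with the arm known. An any-cause count avoids the judgment.

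**Working it through.** **Step 1. The passages side by side.**

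| Place | Role | Cause restriction |
|---|---|---|
| Protocol Table 1, 13.4, 13.4.1, 13.4.2, 13.7 | Endpoint definition and test statistic | None |
| SAP section 6 | Endpoint definition | None |
| Protocol 7.1.3 | Collection list | None; reason recorded |
| Protocol 10.2 | Collection list | None |
| Protocol 13.8 | Planning rate, 12% | None stated |
| Protocol Table 2 | Schedule of Events row | Ambiguous |
| Protocol 10.3 | Follow-up text | Seizure-related |
| SAP section 4 | Design summary | Seizure-related |

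In Table 2 the adjective cannot sensibly govern the whole row, because the row ends with the length of the surgical admission. It may govern readmissions alone, or both readmissions and ED visits. The two restricted statements and the one ambiguous row all describe capture. No endpoint definition is restricted.

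**Step 2. The planned sample size.** Inputs from 13.7 and 13.8: 12% on AED, 25% on no AED, one-sided 0.05, power 80%, equal combined groups, and one interim at half the information with boundaries 2.31015 (reject), 0.48887 (accept) and 1.63351 (final).

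- Fixed design, unpooled variance, per group: (1.645 + 0.842)² × (0.12×0.88 + 0.25×0.75) / 0.13² = 107.2.
- Inflation for the two-stage boundaries, by numerical integration: 1.073. Then 107.2 × 1.073 ≈ 115.06, rounded up to 116 per group, or 232 in total.
- Type I error with these boundaries: 0.0500. Power at 232: 80.3% (unpooled) or 79.3% (pooled).

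The plan's figure of 232 is reproduced for the endpoint as defined.

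**Step 3. Sensitivity to restricted capture.** The documents give no split of encounters by cause, so every split below is an assumption. Method: exact binomial enumeration, 58 then 116 per group, 13.7 boundaries, Z = (p₂ − p₁) / √(2p̄(1 − p̄)/n), where p₁ is the AED rate and p₂ the no-AED rate.

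| Assumption | Captured rate, AED / no AED | AED declared better | Interim stop, AED not better |
|---|---|---|---|
| Full capture | 12% / 25% | 80.5% | 8.7% |
| 75% of events captured in both arms | 9% / 18.75% | 68.4% | 13.2% |
| 50% captured | 6% / 12.5% | 51.2% | 23.0% |
| 25% captured | 3% / 6.25% | 31.7% | 37.0% |
| 4 points of other-cause events lost per arm | 8% / 21% | 87.6% | 5.3% |
| 6 points lost | 6% / 19% | 91.2% | 4.0% |
| 8 points lost | 4% / 17% | 94.8% | 2.7% |

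Rows 2 to 4 assume that the seizure-related share is the same in both arms. Rows 5 to 7 assume that the whole 13-point difference is seizure-related. Power falls under the former and rises under the latter.

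A further case takes equal any-cause totals of 12% with captured rates of 4% and 6%. AED is then declared better 16.9% of the time, against 5.0% with full capture. This needs 12 − 4 = 8 points of other-cause encounters on AED and 12 − 6 = 6 on no AED, a pattern for which the documents give no data.

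**The case against.** The strongest reply is that the operative text already settles the scope. Every endpoint definition is unrestricted, and 10.3 is a short pointer that sends the reader to 10.2, whose list has no cause filter. Recording the reason for each encounter, as 7.1.3 requires, would add little if only seizure-related encounters were captured. SAP section 4 is a summary, and section 6 holds the outcome definition. Side-effect encounters also have a partial backstop: adverse events of special interest are collected for 30 days, and SAP section 7 records whether attention was sought for the listed symptoms.

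Most of this stands. It makes any-cause capture the probable intention and shows that the endpoint definition is not in dispute. It does not remove the conflict, because 10.3 and SAP section 4 still state a narrower scope than the list and outcome they serve. The adverse-event record is no substitute either: under 11.1 and 11.1.1, events outside the special-interest list are not collected, and seeking attention for a symptom is not the same as an ED visit or readmission.

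A reader might infer from the past tense in SAP section 4 that capture really was restricted. The documents do not support that. The paragraph mixes tenses, and section 6 applies no filter. The SAP text after the start of the medical-history part of section 9 was not available for this check, so a clarification there cannot be ruled out.

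**Conclusion.** This is an internal inconsistency in how capture of the primary endpoint is described. Protocol 10.3 and SAP section 4 are wrong as written against 13.4.1 and SAP section 6, and the Table 2 row is ambiguous. If the restricted wording were followed, the data would match neither the stated endpoint nor the unqualified 12% planning rate.

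Two stronger conclusions are tempting, and neither is supported. One is that encounters were in fact missed; nothing in the documents shows this. The other is that the trial is underpowered, or biased towards AED, because of it. The calculated range of 31.7% to 94.8% lies on both sides of the planned 80% and rests wholly on assumed splits, so neither size nor direction can be determined. With the any-cause endpoint kept, N = 232 stands.

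**What to change.** 1. In Protocol 10.3, Table 2 and SAP section 4, replace the seizure-related wording with: all ED visits and hospital readmissions, any cause, within 30 days of MSR, with reason recorded. This matches 7.1.3 and 13.4.1. In Table 2, keep provider communications and length of the surgical admission as separate items.
2. State in SAP section 6 that admitted_ed and hospitalized are any-cause.
3. If data are already collected, confirm and document before analysis which scope the patient calendar and the eCRF captured. Only if capture was restricted, check hospital records, which 12.3.1 lists as source documents, for missed encounters in all arms.

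The cost is wording in three places and one SAP sentence, plus a check of two forms if data exist. No new procedure is needed, because 7.1.3 already collects readmissions and ED visits with their reasons. The sample size and interim boundaries are unaffected.

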10.4 End of Study

The study will be considered complete once enrollment has been met, follow-up evaluations on all subjects have been conducted, and data analysis is concluded. The study may also be terminated early for any reason by the PI-sponsor.

Subjects that are lost to follow-up will be documented in the patient record and in the REDCap™ database. In the REDCap™ database, the subject will be marked as “Patient Status Unknown,” along with a corresponding explanation, if any. This status may also be documented on the “Off Study Form” in the REDCap™ database.

10.5 Early Withdrawal of Subject(s)

10.5.1 Criteria for Subject Discontinuation from the Study

Subjects may voluntarily withdraw from the study at any time. The primary investigator (PI) may also withdraw a subject from the study at any time based on his/her discretion. Reasons for PI-initiated withdrawal may include, but is not limited to the following:

- Non-compliance of the subject
- Administrative issues
- Concerns for patient safety

10.5.2 Replacement of Non-evaluable

A subject who withdraws study participation between randomization and the MSR will be excluded from primary analysis. An additional patient will be randomized to the study to replace that subject to meet the sample size requirements.

10.6 Study Assessments

Study assessments listed here are obtained per standard of care and are only documented for purposes of eligibility assessment.

10.6.1 Medical History

Standard medical history will be obtained and documented per institutional guidelines.

10.6.2 Physical Exam

Standard physical exam and neurological assessment will be conducted and documented per institutional guidelines.

10.6.3 Laboratory Evaluations

The timing of standard laboratory assessments that will be obtained during the course of the study is given in the Schedule of Events Table 2 in Section [10](#). A list of each evaluation and what they include is below.

- CBC with differential
- CMP
- Urine pregnancy test, if appropriate (serum pregnancy test if unable to obtain urine)

11 SAFETY MONITORING AND REPORTING

The PI is responsible for the identification and documentation of adverse events and serious adverse events, as defined below. At each study visit, the PI or designee must assess, through non-suggestive inquiries of the subject or evaluation of study assessments, whether an AE or serious adverse event (SAE) has occurred.

11.1 Adverse Events

An AE is any untoward medical occurrence in a subject receiving study drug and which does not necessarily have a causal relationship with this treatment. An AE can therefore be any unfavorable and unintended or worsening sign (including an abnormal laboratory finding) or symptom temporally associated with the use of the AED, whether or not related to use of the AED.

From the time the subject initiates AED therapy through the time the subject is off study (as defined in Section [7.3](#)), all AESIs must be recorded in the REDCap™ database AE electronic Case Report Form (eCRF). Adverse events which are not an AESI will not be collected.

AESIs will be assessed according to the Common Terminology Criteria for Adverse Events (CTCAE) version 4. If CTCAE grading does not exist for an AESI, the severity of the AESI will be graded as mild (1), moderate (2), severe (3), life-threatening (4), or fatal (5).

Attribution of AEs will be indicated as follows:

- Definite: The AE is clearly related to the study drug
- Probably: The AE is likely related to the study drug
- Possible: The AE may be related to the study drug
- Unlikely: The AE is doubtfully related to the study drug
- Unrelated: The AE is clearly NOT related to the study drug

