7.1.4 Adverse Events of Special Interest (AESI)

The occurrence of adverse events of special interest (AESIs) will be recorded only for the 30-day post-procedure phase.

AESIs for this study will be graded using the National Cancer Institute's (NIH) Common Terminology Criteria for Adverse Events (CTCAE) v4 and are the following: any grade of seizure, dizziness, somnolence, cognitive

disturbance, nausea, vomiting, ataxia, nystagmus, suicidal ideation, suicide attempt, anxiety, irritability, depression, psychosis and personality change (e.g. aggression).

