7.3 Definition of Evaluable Subjects, On Study, and End of Study

Any patient that has been consented and randomized to the trial will be included in all analyses with the exception of those deemed non-evaluable as described in Section [10.5.2](#).

Subjects will be considered on study once they have signed the informed consent form.. Subjects will be considered off study when they have been evaluated approximately 6 to 10 weeks post MSR and once their calendar has been submitted.

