13.5 Secondary objectives

This study has one secondary objective which is to assess the safety and tolerability of LCM and LEV.

Adverse events will be assessed according to the NCI Common Toxicity Criteria for Adverse Events (CTCAE) version 4. For each type of toxicity, the maximum grade experienced by the patient will be summarized with frequency distributions based upon all AESIs. Of particular interest are those adverse events of special interest (AESI), as defined in section [7.1.4](#), that occur within 30 days after MSR.

The percentage of patients experiencing any grade adverse events of special interest within 30 days of MSR will be summarized in each of the 3 treatment arms, and compared using chi-square tests. If AED is shown to have fewer re-hospitalizations or ED visits, then a pairwise comparison of LCM and LEV is of particular interest.

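### Section 11.1 conflicts with the plan's 30-day rule for recording AESIs and is worded in a way that does not fit the no-AED arm; the output exposed is the maximum-grade table

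*Protocol*

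**What the plan says.** Section 11.1 makes AESI recording mandatory "From the time the subject initiates AED therapy through the time the subject is off study". It refers to section 7.3 for the end point: "Subjects will be considered off study when they have been evaluated approximately 6 to 10 weeks post MSR", with the calendar also handed in. The same section opens its definition with "An AE is any untoward medical occurrence in a subject receiving study drug", ties events in time to use of the AED, and offers an attribution scale running only from clearly related to clearly unrelated to the study drug.

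Section 7.1.4 sets a different rule: "The occurrence of adverse events of special interest (AESIs) will be recorded only for the 30-day post-procedure phase". Its list begins with "any grade of seizure, dizziness, somnolence" and is not restricted by arm. The Table 2 footnote, sections 10.1, 10.2 and 10.3, and SAP sections 4 and 7 also use 30 days.

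Section 13.5 describes two outputs. In the first, "the maximum grade experienced by the patient will be summarized with frequency distributions based upon all AESIs", with no day limit; the text then singles out AESIs within 30 days of MSR as the ones of main interest. The second is the percentage of patients with any-grade AESIs within 30 days, which "will be summarized in each of the 3 treatment arms, and compared using chi-square tests".

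**The concern.** The two recording rules cannot both be followed. One says that AESIs must be entered until the subject is off study; the other says that they are entered only for 30 days. Staff working from 11.1 and staff working from 7.1.4 would build different databases.

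The 11.1 wording also depends on arm. Its definition and its recording start presuppose an AED. Read alone, it gives a control patient who never takes one neither a definition nor a start date, while patients on LCM or LEV are recorded for well over 30 days.

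What is at stake is the comparability of the maximum-grade table, which serves the protocol's only secondary objective, and of the database that the PI and statistician review for trends under 11.1.1. If 11.1 were followed literally, longer recording on drug and thinner recording on control would both tend to make the drugs look worse.

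**Working it through.** **Arm sizes.** Protocol 13.8 gives N = 232 and allocation 1:1:2 (LCM : LEV : no AED). 232/4 = 58, 232/4 = 58, 232/2 = 116, matching the 116 and 116 in the 13.7 table. As a check on 232 itself, take 12% against 25%, one-sided alpha 0.05, 80% power and the stated two-stage boundaries. The required N is then 230.1 with unpooled variance and 236.7 with pooled variance, so 232 is consistent. Nothing in this point changes the sample size. The share of patients whom the 11.1 wording does not fit is 116/232 = 50%.

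**Window length.** Inputs: off study at about 6 to 10 weeks after MSR (7.3); AED start up to 48 hours before incision (7.1); 30-day rule (7.1.4).

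- End of the 11.1 window: 6 × 7 = 42 days to 10 × 7 = 70 days after MSR.
- Beyond day 30: 42 − 30 = 12 days to 70 − 30 = 40 days.
- Adding up to 2 days before incision: 42 + 2 = 44 to 70 + 2 = 72 days.
- Ratio to 30 days: 44/30 = 1.47 to 72/30 = 2.40.
- A patient cross-tapered to the new drug a week before surgery (7.1): 42 + 7 = 49 to 70 + 7 = 77 days.

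**Test cases under each rule.**

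| Event | 11.1 | 7.1.4 |
|---|---|---|
| AESI on LCM or LEV, day 35 after MSR | must be entered | excluded |
| AESI on LCM or LEV, day before incision | must be entered | excluded |
| AESI in a control patient never given an AED, day 10 | no definition or start applies | entered |
| AESI in a control patient given the one permitted mapping dose, day 10 | arguably entered, because an AED was started | entered |
| First seizure in a control patient before any AED, day 5 | before the window opens | entered |

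**Which outputs depend on the choice.** The any-grade percentage carries its own 30-day limit in Table 1 and in 13.5, so late or pre-operative entries drop out of it under either rule. The maximum-grade table carries no limit, and 13.5 contrasts it with the 30-day subset, so an unrestricted table is a natural reading. The 11.1.1 review draws on the whole AESI database and likewise has no day limit.

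**Which section is out of line.** Seven places use 30 days for recording or for the outcome definition: 7.1.4, the Table 2 footnote, 10.1, 10.2, 10.3, SAP 4 and SAP 7. Only 11.1 differs, so 11.1 is the section to correct.

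**The case against.** The strongest reply is that this is a stray paragraph outvoted by the rest of the plan. The Table 2 footnote limits the endpoint data entered in source documents and database to 30 days, and SAP section 4 states in the past tense that adverse events were collected for 30 days. If that is what happened, the conflict had no effect. This stands, and it caps the importance of the point. It does not remove the contradiction, because 11.1 is the section on AE recording and is worded as an obligation.

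A reader might infer that control-arm AESIs go uncollected. The documents do not support that. Only non-AESI events are left out, so the list in 7.1.4 is the working definition, and it is not restricted by arm. Table 2 schedules an adverse event check for everyone, 13.5 reports all three arms, and SAP section 7 sets out its AESI items without regard to arm. The gap lies in the wording of 11.1.

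Nor would control-arm seizures be lost. Seizure activity is collected under 7.1.3, analysed by arm under 13.6.4, and listed as its own outcome (item 6) in SAP section 7.

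A reader might also think the window open-ended for high-grade glioma, because 7.1.3 does not date the post-radiation visit. Table 2 and 10.2 place that visit in weeks 6 to 10.

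Finally, it is tempting to express the longer window as an excess in event percentages. The documents give no 30-day AESI rates by arm. The 10% figure in 5.2.8 is for LEV 500 mg BID rather than the trial's 1000 mg BID, and 5.2.5 says LCM events are more apparent during initial titration, which argues against a constant rate. Setting 11.1 for the drug arms against 7.1.4 for controls would also mix two rules that neither section combines. No such figure is justified.

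**Conclusion.** The point holds as an internal contradiction that should be corrected. Section 11.1 sets a recording window of about 44 to 72 days (42 to 70 after MSR plus up to 2 before) where the rest of the plan sets 30, and its wording does not fit 116 of 232 patients. The outputs exposed are the descriptive maximum-grade table and the trend review.

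The primary endpoint is untouched, and the 30-day any-grade AESI percentage is not affected by the window conflict. There is no general gap in oversight: section 11 requires AE assessment at each visit, and 12.1 has the PI monitor adverse events continuously.

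The effect on the table cannot be sized from the documents. It is nil if the 30-day rule was used throughout. The conclusion assumes that the off-study visit falls within the stated 6 to 10 weeks. The SAP text available here ends at the demographics section, so whether its analysis section already limits the maximum-grade table to 30 days has to be checked.

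**What to change.** - **11.1:** define and record AESIs identically for every randomized subject who undergoes MSR, in all three arms and whether or not an AED is taken, for days 0 to 30 after MSR. Add a category for not applicable (no AED) to the attribution scale.
- **13.5 and SAP section 7:** state that the maximum-grade table uses the same days 0 to 30, unless the SAP's analysis section already says so.
- **Database:** check AESI onset dates once. List any events before MSR or after day 30 separately by arm, outside the comparison.

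The SAP describes collection as already done, so the onset check and the day limit on the table are likely to matter most in practice. The cost is a few wording changes and one data check, with no added visits, patients or data collection. The downside is that AESIs before MSR or after day 30 stay out of the summary tables; serious and unexpected events remain reportable under 11.2.1.
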